#### **9.7.3.3 Competing Risk Analysis**

Events (e.g., death due to causes other than COVID-19) that may make it impossible for the event of interest to occur (e.g., hospitalisations for COVID-19) act as competing events in the analysis of certain outcomes. The relevance of competing events increases when the study population is old or sick (a plausible target population of the COVID-19 vaccine) or when the follow-up is long. The use of specific methodology to handle competing events can help in the accurate interpretation of the study results.

Thus, competing risk in survival analysis will be taken into account in an additional HR estimation.

## **9.7.4 Subgroup, Sensitivity, and Exploratory Analyses**

### **9.7.4.1 Conducting Subgroup Analyses**

The primary analyses will be stratified by clinically meaningful subgroups found or suspected linked with the prognostic of the covid-19 infection, which will include the following:

- Old patients (i.e. aged  $\geq 80$  years)
- Patients with cardiovascular disease,
- Patients with diabetes,
- Patients with chronic pulmonary disease (COPD, asthma, etc);
- Patients with cancer
- Patients who are immunocompromised
- Pregnant women
- Smoker patients (suspected linked with the prognosis in some studies)
- Patients with obesity (BMI for obese category)
- Patients vaccinated against Influenza in the fall-winter season 2020-2021 this analysis seeks to reduce unmeasured confounding by health care access, adherence to recommendations, and preventive health care behaviours [9,25].
- Geographic region (if sufficient sample size in all regions)

Also, the primary analyses will be stratified by calendar months in order to observe in periods with stronger confusion due to individuals prioritisation (i.e. channelling of atypical patients in the period immediately following approval [44]). For instance, confusion could be strongest when the vaccinations occurred only for health care workers and nurse home residents. Background anamnesis may not be systematically recorded in primary care for those groups and we do not have information about the job or nursing home residing for selecting non-vaccinated individuals based on those criteria (or matching by it), thus the compared unvaccinated cohort may have less probability of vaccination or outcome, respectively.

Stratifying by months, we could observe differences in effectiveness that could be affected by a higher confusion in months previous to the date when vaccination was recommended for a broad general population.

### **9.7.4.2 Varying Outcome Definitions**

The validity and precision of COVID-19 diagnosis coding is currently unknown, thus those recorded codes will be extracted for comparison to lab test as gold-standard of the infection.

If the number of patients with recorded codes for COVID-19 infection (so-called 'possible cases') are far from those identifies through lab test (so-called 'confirmed cases'), a sensitivity analysis for vaccine effectiveness estimation will be performed including all of them.

### COVID-19 Diagnosis Coding

COVID-19 diagnosis coding has been introduced recently into the code systems included in BIFAP and linked registries (International Classification of Primary Care (ICPC)(19), International Classification of Diseases (20), 9th and 10th Revision (ICD-9 and ICD-9)) as follows:

ICPC	Infección debida a coronavirus NE	A77.01
ICD9MC	Infección por coronavirus asociada a SARS	079.82
ICD10 ES	COVID-19 (*)	U07.1

(\*) Nota: hasta jun-2020 la equivalencia estuvo establecida a "Infección debida a coronavirus, no especificada" (código B34.2)

Those codes will be distinguished from subcodes for confirmed or suspected cases [70-71]:

ICPC	Contactos/exposición a otras enfermedades víricas transmisibles	A23.19
CIE9MC	Contacto/exposición a otras enfermedades víricas	V01.79
CIE10 ES	Contacto y (sospecha de) exposición a otras enfermedades víricas transmisibles	Z20.828

Those codes were introduced in 2020 (19,20) and ready for codification from the start of the vaccination period.

Also, in order to estimate the validity and precision of COVID recorded diagnosis, the following parameters will be estimated to further used in research studies in BIFAP in comparison with lab results as gold-standard:

- Positive Predictive Value (i.e. PPV=confirmed covid/diagnosis code)
- Sensitivity (S=diagnosis code/confirmed covid).

#### 9.7.4.3 Correcting for Differential Outcome Misclassification

Since no validation studies are planned for the outcome (identified through lab results considered gold-standard in the clinical practice), quantitative bias analyses will not be performed to evaluate the potential impact of differential misclassification of the outcome on the observed study estimate. As a proxy, external comparison of incidences (overall, by region, calendar dates and age) will be performed as aforementioned. This may be mentioned as limitation although lab result are even clinically used as confirmatory infection.

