## **8 Research Question and Objectives**

This study addresses the research question of whether vaccinations with new licenced COVID-19 vaccines, (Comirnaty, Moderna, AstraZeneca's and Janssen and subsequently

approved vaccines in the EU during the data collection), are effective in reducing the burden of COVID-19 in Spain in comparison with no vaccination periods.

**Primary objective** is to evaluate the effectiveness of each COVID-19 vaccine in reducing the covid-19 infections (confirmed through test and regardless the prognosis and clinical phenotype (i.e. whether symptomatic or asymptomatic, mild or severe).

**Secondary objectives** of this study will be splitting the effectiveness

- by the following outcomes:
  - asymptomatic (defined as a positive test (whether PCR or antigens) without recorded symptoms in primary care +/-14days of the date the sample was taken). Note: In epidemiological vigilance protocols, among asymptomatic patients, isolation must be maintained till 10 days after the date when the sample was taken.
  - symptomatic (defined as positive test (whether PCR or antigens) with recorded symptoms in primary care or Hospitalisations/Intensive care unit (ICU) admissions +/-14days of the date the sample was taken (or at anytime linked with the test result))
  - Hospitalisations/Intensive care unit (ICU) admissions for COVID-19 at anytime linked with the test result or within +/-14days of the date the sample was taken (if hospitalisation was recorded in primary care clinical profile)
  - All-cause mortality as a recorded death with COVID 19 listed as an underlying cause of death on cause-of-death registers, or a death during a hospitalisation, with COVID-19 as a listed diagnosis, or a death within a specified time period (e.g., 28 days) after a diagnosis or hospitalisation for COVID 19.
- over clinically meaningful subgroups (old people; patients with cardiovascular disease, diabetes, or chronic pulmonary disease, chronic renal impairment, treated cancer, patients with a history of transplantation, Down Syndrome found linked with the prognostic of the covid-19 infection; as well as smoking, males and obesity suspected linked with the prognosis in some studies)
- along the time since complete vaccination (up-to 3 months, 6 months and ever after).

A feasibility evaluation will be conducted before the start of the study to evaluate the availability of key data elements and the appropriateness of the study design.

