#### **COVID-19 Test results (PCR, antigens, etc.)**

Test results for coronavirus will be linked with PC eHR. For effectiveness analysis, cases will be positive covid infections recorded in that registry that may be confirmed through positive PCR, Antigens or any other confirmatory criteria established by clinical protocols (that definition is out of the scope of the current study).

Laboratory-confirmed infection is considered gold-standard to identify cases for the main analysis, thus no predictive values will be estimated. As explained below, identification of so-called 'possible' covid cases recorded only through diagnosis coding (without lab information) will be performed in a Sensitivity analysis (Section 9.7.4.2).

Also, an estimation of the concordance between the observed incidences in BIFAP and those 'expected' will be performed (i.e. external validation) as a proxy for the accurateness to identify cases in BIFAP and discussion of potential reasons if differences would be present.

The 'expected' cumulative incidences will be calculated by dividing the COVID cases reported daily to RENAVE (base de datos de vigilancia epidemiológica; by calendar period, region and age) by the population reported in the Spanish National Statistics Institute for that year [73]. Access to RENAVE will be available by one of the institution collaborating in the current study [74].

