Health care utilisation in the year before time zero and updated will be evaluated as measures of health care-seeking behaviour, overall health status, and access to health care. Additionally, short-term health care utilisation in the 2 weeks before and including time zero and updated will be recorded separately, as short-term markers of current health status may influence individuals' vaccination decisions. Considered variables will include the following:

- Primary care utilisation (number of visits to PC)
- Influenza vaccination (number in the previous 5 years)
- Other vaccinations (number in the previous 5 years)
- COVID-19 tests (total number)

Frailty has been demonstrated as a confounder of vaccine-outcome associations in older adults [5,6,9]. Additional personal characteristics demonstrated to be associated with frailty [6,31,32] should be included as confounding factors, and may include the following:

[figure not shown]
- Wheelchair use
- Home hospital bed
- Paralysis
- Parkinson's disease
- Skin ulcer

- Weakness
- Stroke/brain injury
- Ambulance transport
- Dementia
- Difficulty walking
- Home oxygen
- Rehabilitation care
- Psychiatric illness
- Sepsis
- Heart failure
- Podiatric care
- Bladder continence
- Diabetes complications
- Arthritis
- Coagulation deficiencies
- Vertigo
- Lipid abnormalities

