The validity of coding for future COVID-19 vaccines—including the ability to distinguish between separate products—or COVID-19 outcomes is unknown at this time, and the likelihood of missing data on specific vaccine brand may be high. Misclassification of vaccine exposure, outcome status, or covariates is possible in existing health care data not collected for research purposes. Information about COVID-19 infection (through test results or codes) may not be captured reliably in databases. Additionally, COVID-19 testing is not systematic, and laboratory confirmation of case status may not be available for many patients. Currently, bias may be minimised since COVID 19 testing becomes near universal and repeated with individuals, with similar testing capacity and practice across regions, though. Since we will not have any better gold-standard for case status than the information about confirmed covid-19 infection through lab results (used for case definition in the current study) its precision will not be evaluated but with the expected external incidences published by the Health authorities.

Also, we consider that if COVID misclassification occurred it would be similar in both, vaccinated and unvaccinated groups, however surveillance or detection bias (different likelihood of screening or testing for COVID between the groups) cannot be discarded. If vaccinated individuals had less likelihood of screening or test than unvaccinated, we would artificially observe more cases among unvaccinated, directing toward a biased higher vaccine effectiveness estimation.

Data from multiple regions and sources will be merged in BIFAP and included in the study, thus, there may be variation in the capture and recording of various clinical elements. Additionally, different types of data sources will be used (e.g., records from general practice and lab results from other registers) as well as different coding systems, then variables defined in different data sources may not exactly represent the same concept across data sources. Thus, heterogeneity of vaccine effectiveness estimates across data sources may be due to the underlying heterogeneity of confounding control, misclassification, or other data source factors rather than true differences in vaccine effectiveness.

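### The RENAVE comparison offered in place of a bias analysis is not split by vaccination status, so it cannot show whether vaccinated and unvaccinated people were tested differently

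*Protocol*

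**What the plan says.** Section 9.7.4.3 carries the heading of a correction for differential outcome misclassification. It states that "quantitative bias analyses will not be performed to evaluate the potential impact of differential misclassification of the outcome on the observed study estimate", because no validation study of the outcome is planned and laboratory results are treated as the gold standard. It then offers a substitute: "As a proxy, external comparison of incidences (overall, by region, calendar dates and age) will be performed as aforementioned".

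Section 9.1.1.2, under the COVID-19 test results, describes that comparison: "an estimation of the concordance between the observed incidences in BIFAP and those 'expected' will be performed", and gives its purpose "as a proxy for the accurateness to identify cases in BIFAP". The expected incidence comes from "dividing the COVID cases reported daily to RENAVE (base de datos de vigilancia epidemiológica; by calendar period, region and age") by National Statistics Institute population figures. Vaccination status is not a stratum in either section.

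On the threat itself, Section 9.9 says that "surveillance or detection bias (different likelihood of screening or testing for COVID between the groups) cannot be discarded", that testing is not systematic, and that less testing of vaccinated people would inflate effectiveness. The comments to Section 12 of the ENCePP checklist add the opposite direction.

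Section 8 defines one secondary outcome as "asymptomatic (defined as a positive test (whether PCR or antigens) without recorded symptoms in primary care" within 14 days either side of the sample. The main outcome in Section 9.3.3.1 counts confirmed infections whatever the symptoms. Section 9.3.4 lists "COVID-19 tests (total number") among the health care utilisation variables, measured before time zero and updated. Section 9.7.3.2 selects adjustment variables by backward stepwise significance testing.

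**The concern.** Two errors can affect a laboratory-defined outcome. A positive result may be false, or an infection may never be tested. The gold-standard argument answers the first. Differential misclassification in this study is mainly the second: whether an infected vaccinated person is as likely to be tested as an infected unvaccinated person.

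The substitute check does not bear on that question. A stratum of one region, one week and one age band pools both groups, so its incidence is a single number that many combinations of testing rates can produce. The external figure also depends on who was tested and reported, so the same testing difference can be present on both sides of the comparison.

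At stake is first the effectiveness against asymptomatic infection. Without symptoms to prompt a test, such an infection is recorded only if the person is tested for another reason, so a testing difference passes directly into the hazard ratio. The primary outcome, which mixes symptomatic and asymptomatic positives, takes up part of it. Hospitalisation should be less affected.

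**Working it through.** **The plan's own figure.** The plan gives no figure for detection bias. The nearest is Table 1, which puts the probability that the upper 95% limit of the risk ratio falls below 1 at 1 in all eight rows. It reproduces. For the Janssen row at 2:1, N = 7,720,843, unexposed risk 0.0006057 and RR 0.331:
- exposed cases = (7,720,843/3) × 0.0006057 × 0.331 = 516; unexposed cases = (2 × 7,720,843/3) × 0.0006057 = 3,118
- SE of ln RR ≈ √(1/516 + 1/3,118) = 0.048; −ln(0.331)/0.048 − 1.96 ≈ 21, so the probability is 1.

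This concerns random error only and says nothing about detection.

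**Effect on the estimate.** Let r be the chance that an infection is tested in vaccinated relative to unvaccinated people. The documents do not give r or the true effectiveness; both are assumed. For an outcome seen only through testing:

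VE_obs = 1 − (1 − VE) × r

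- True VE 60%, r = 0.5: 1 − 0.40 × 0.5 = 80%
- True VE 60%, r = 0.75: 1 − 0.40 × 0.75 = 70%
- True VE 60%, r = 1.5: 1 − 0.40 × 1.5 = 40%
- True VE 0%, r = 0.5: 1 − 1 × 0.5 = 50%

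**Effect on the planned check.** Let v be vaccine coverage (assumed) and u the detection level in the unvaccinated. Detected total incidence is proportional to u × [(1 − v) + v(1 − VE)r]. With VE 60%:

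| v | r | Total relative to r = 1, u fixed | u that restores the total | VE_obs |
|---|---|---|---|---|
| 10% | 0.5 | 0.92/0.94 = 0.979 | 1.022 | 80% |
| 10% | 1.5 | 0.96/0.94 = 1.021 | 0.979 | 40% |
| 30% | 0.5 | 0.76/0.82 = 0.927 | 1.079 | 80% |
| 30% | 1.5 | 0.88/0.82 = 1.073 | 0.932 | 40% |
| 50% | 0.5 | 0.60/0.70 = 0.857 | 1.167 | 80% |
| 50% | 1.5 | 0.80/0.70 = 1.143 | 0.875 | 40% |

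At 10% coverage the total moves by about 2% while the observed effectiveness runs from 40% to 80%. At any coverage shown, a modest change in u leaves the total exactly where it was. A total not split by vaccination status therefore does not identify r.

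**Why the overall testing ratio is not r.** A vaccine that prevents symptoms also removes symptom-driven tests. Suppose screening is equal in both groups, 30% of tests in the unvaccinated are prompted by COVID-19 symptoms, and the vaccine prevents 60% of these. The overall testing ratio is 0.70 + 0.30 × 0.40 = 0.82, although asymptomatic infections are detected equally. Dividing a correct asymptomatic HR of 0.40 by 0.82 gives 0.49, so a correct 60% would be changed to 51%.

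**The case against.** Four arguments stand against the point.

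- **The plan does look at testing.** A reader might infer that nothing in the protocol compares testing between the groups. The documents do not support that. Test counts are collected and updated (Section 9.3.4), characteristics are described by exposure group and period (Section 9.7.1), and the count can enter the model (Section 9.7.3.2). But the count is only a stepwise candidate, and Section 9.7.4.3 does not use it.
- **The threat is disclosed.** This is so. Section 9.9 and the checklist name it, Section 9.7.4.3 allows that it may be reported as a limitation, and checklist item 10.6 is answered no. A reader might infer that detection bias was overlooked, or that agreement with RENAVE is bound to be misread as reassurance. The first is contradicted by the text and the second is conjecture. What stands is that the section names a substitute that cannot do the task in its heading.
- **Other analyses limit the exposure.** Influenza-vaccinated patients are analysed separately, brands are compared head to head, coded cases may be added, and hospitalisation and death depend less on discretionary testing. Section 9.9 also expects testing to become near universal. These help, but none estimates the testing difference, and a change in testing brought about by vaccination arises after time zero.
- **Such detail belongs in an analysis plan.** Table layouts do. The statement that bias analysis will not be done, and the choice of substitute, are fixed in the protocol.

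It is also fair that the recorded asymptomatic outcome is not purely asymptomatic. Section 9.3.3.2 notes that mild illness without a care visit is counted there, so the simple formula is an approximation.

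**Conclusion.** The point holds, in a limited form. The comparison with RENAVE can speak to overall completeness of case capture, which is the purpose that Section 9.1.1.2 gives it. It cannot speak to differential misclassification, for which Section 9.7.4.3 uses it.

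The size of any actual bias cannot be established from the documents: r, coverage and true effectiveness are all assumed. Within r = 0.5 to 1.5 and a true effectiveness of 60%, an outcome detected purely by testing could show anything from 80% to 40%. The shift in the primary outcome would be smaller if only its asymptomatic part is affected, by an amount that depends on a share the documents do not give. Nothing here shows that testing did differ, or in which direction.

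A reader might also infer that the asymptomatic estimate should be divided by the observed testing-rate ratio. That is not supported, because vaccination itself lowers symptom-driven testing. This is a change that should be made; it does not undermine the design.

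**What to change.** In Section 9.7.4.3:

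1. Keep the RENAVE comparison, described only as a check on overall completeness of case capture.
2. Report COVID-19 testing rates by vaccination status, exposure period and brand, separating tests without recorded symptoms where the data allow.
3. Replace the statement that bias analysis will not be performed with a sensitivity analysis of asymptomatic and primary effectiveness over a stated range of r, using VE = 1 − HR_obs/r for the asymptomatic outcome. For the primary outcome, apply r to cases without recorded symptoms, and state that assumption. This step needs no new data.
4. Where regions supply negative results, add percent positive and a first negative test as a negative-control outcome. Make this conditional: the abstract describes the linked registry as one of positive results, while Sections 9.3.4 and 9.4 suggest that all tests may be available.
5. Do not present an effectiveness corrected by the overall testing-rate ratio.

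The cost is a few additional tables and one sensitivity analysis. The downside is that the negative-test check may be confined to regions that supply all results.

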### **9.7.5 Missing Data**

Missing data for the information about COVID-19 vaccinations, i.e. date of administration, type/brand of vaccine, dose order (whether 1st or 2nd dose), may happen due the workload. However, due the importance of knowing the effect of the vaccinations in the pandemic we expect the health professional properly record all required data.

The distribution and pattern of missingness (i.e. missing completely at random or missing at random) will be assessed [49]. The pattern missing not at random (MNAR) may be derived from external data on the doses distributed by region and among prioritised groups. If amount of missing is relevant, single stochastic imputation will be performed based on determinant of both, missing data and the value of the variable with missing data. Mainly, calendar month or week, region and prioritised group will be tested as determinant of missing and will established for the imputation. Multiple imputation correcting by the variance is a more complex approach (even more using a time-varying data source) and may not be worthy if simple determinants are identified.

No imputation are planned for missing data in potential confounders (i.e. BMI or smoking use). In order to all individual contribute to the analysis, a missing category will be established for patients with missing data. If those variables suggest poor confusion in the regression models, they will be removed as confounders for the final models [72].

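### If missing vaccine brand is filled by a single stochastic imputation, brand-specific effectiveness is either pulled together or given intervals that are too narrow, depending on the imputation model

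*Protocol*

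**What the plan says.** Section 9.7.5 names the variables at issue: "Missing data for the information about COVID-19 vaccinations, i.e. date of administration, type/brand of vaccine, dose order". It says that the distribution and pattern of missingness will be assessed and that, where the amount missing is relevant, "single stochastic imputation will be performed based on determinant of both, missing data and the value of the variable with missing data". The amount that counts as relevant is not defined. On predictors it says: "Mainly, calendar month or week, region and prioritised group will be tested as determinant of missing and will established for the imputation". On the alternative it says: "Multiple imputation correcting by the variance is a more complex approach (even more using a time-varying data source) and may not be worthy", and the sentence ends with a condition, namely that simple determinants are identified. No other allowance for imputation uncertainty is described.

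On extent, section 9.7.5 expects health professionals to record everything required, whereas section 9.9 warns that "the likelihood of missing data on specific vaccine brand may be high".

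For confounders section 9.7.5 says: "No imputation are planned for missing data in potential confounders (i.e. BMI or smoking use"). Instead, "a missing category will be established for patients with missing data", and such variables are dropped if they show little confounding in the models.

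The imputed variables are central. Section 8 makes the effectiveness of each vaccine the primary objective. Section 9.1.1.4 runs the main analysis by brand and sets time zero, for the vaccinated person and the matched unvaccinated persons, at the first-dose date. Section 9.1.1.5 adds head-to-head comparisons between vaccines.

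**The concern.** A single imputed value is one random draw that the analysis then treats as data. That would matter little for a minor covariate, but here the drawn value decides which vaccine a person's follow-up and events are credited to.

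If brand is drawn without regard to whether the person became a case, some cases on a less effective vaccine are credited to a more effective one and the reverse. The estimates then move towards their average. If brand is drawn with the outcome in the model, that bias goes away, but the uncertainty of the draw is not in the standard error.

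The named predictors are also incomplete. Sections 9.7.4.1 and 9.9 say that job and type of residence are not available, so prioritised group can be only partly observed. Calendar time of vaccination is itself unknown when the date is missing.

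At stake are the brand-specific primary estimates, their intervals and the head-to-head contrasts.

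**Working it through.** **Inputs from the protocol.** Table 1 (section 9.5): risk 0.0006057 per 14 days in the unexposed; RR 0.05 (Pfizer/BioNTech), 0.059 (Moderna), 0.296 (Oxford/AstraZeneca), 0.331 (Janssen); 7,720,843 persons. Section 9.3.1: ten unvaccinated per vaccinated person.

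**Assumptions, not in the documents.** 1,000,000 vaccinated; brand shares 65%, 10%, 20% and 5% in the order above; 12 weeks of follow-up (six 14-day periods); brand missing completely at random in 5% to 30%; predictors that do no better than the overall brand shares.

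**1. The plan's own figure.** Section 9.7.5 gives none. Table 1 gives a probability of 1 that the upper 95% limit is below 1.00, and all eight rows reproduce. Example, Pfizer/BioNTech at 1:1: exposed events 7,720,843/2 × 0.0006057 × 0.05 ≈ 117; unexposed events ≈ 2,338; SE of log RR = √(1/117 + 1/2,338) ≈ 0.095; upper limit = 0.05 × exp(1.96 × 0.095) ≈ 0.06.

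**2. Outcome not in the imputation model.** With a fraction p of brand missing, the apparent RR is (1 − p) × RR + p × RR_avg, where RR_avg = 0.65 × 0.05 + 0.10 × 0.059 + 0.20 × 0.296 + 0.05 × 0.331 = 0.114. At p = 20%:

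- RR 0.05: 0.8 × 0.05 + 0.2 × 0.114 = 0.063, so VE 95% reads 93.7%.
- RR 0.296: 0.8 × 0.296 + 0.2 × 0.114 = 0.260, so VE 70.4% reads 74.0%.
- The contrast between these two vaccines falls from 0.296/0.05 = 5.9 to 0.260/0.063 = 4.1.

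In simulation the standard errors were about right (ratio of naive to true SE 0.98 to 1.02 at 20%), but because of the bias the 95% intervals covered 23% (Pfizer/BioNTech), 84% (Moderna), 55% (Oxford/AstraZeneca) and 84% (Janssen) of the time. At 5% missing, coverage was 89–95%.

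**3. Outcome in the imputation model.** VE was unbiased, but the naive intervals were too narrow:

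| Missing brand | Naive SE / true SE | Coverage of 95% CI |
|---|---|---|
| 5% | 0.96–0.97 | about 94% |
| 10% | 0.89–0.97 | 92–94% |
| 20% | 0.82–0.91 | 90–92% |
| 30% | 0.73–0.85 | 86–90% |

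As a cross-check, one proper imputation with fraction of missing information g has ratio √((1 − g)/(1 + g)). At g = 0.2 this is √(0.8/1.2) = 0.816, close to the lower end of the 20% row.

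**4. Twenty imputations with the outcome, combined by Rubin's rules.** Coverage was 94–97% for all four brands at 5–30% missing, with no bias in VE.

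**5. Missing category for confounders (secondary).** The residual confounding RR was approximated as the full confounding RR raised to the missing share. Assumed: prevalence 30–40% in the vaccinated against 20% in the unvaccinated, HR 1.5–3, 10–50% missing. Worst case: (1 + 0.4 × 2)/(1 + 0.2 × 2) = 1.286, and 1.286^0.5 = 1.134. VE 70.4% then reads 1 − 0.296 × 1.134 = 66.4%. Over the whole range VE 70.4% reads 66.4–70.3%, and VE 95% reads 94.3–95.0%.

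**The case against.** The best defence is that the text is conditional. Imputation follows only if missingness is relevant, after its pattern has been examined, and multiple imputation is set aside only if simple determinants are found. Section 9.1.1.3 expects date, dose, brand and batch for each administration, from a compulsory linkage used for official coverage figures. The warning in section 9.9 stands in a sentence that opens with the coding of future vaccines. The predictor list is introduced as the main one and does not rule out the outcome. An SAP, not shown here, may complete the model. If the predictors determine brand well, both harms shrink.

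Much of this stands. A reader might infer that the intervals will be too narrow and the estimates attenuated at the same time. The documents do not support that: the two faults belong to different imputation models. Nor do they support reading the protocol as having waived variance correction outright, or as certain to impute.

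What remains is that single imputation is the stated method once triggered, the trigger has no threshold, and neither version of the imputation model gives valid inference without further work.

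On confounders, section 9.7.5 cites a study of missing-data strategies for its approach, and imputing BMI or smoking would rest on a missing-at-random assumption that selective recording in primary care makes doubtful. A reading that the missing category leaves serious confounding is not supported: under the assumptions above the residual is modest, above all where VE is high.

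**Conclusion.** The point holds, conditionally. If the imputation in section 9.7.5 is triggered, the brand-specific results are biased towards each other when the outcome is left out of the model, or have intervals that are too narrow when it is included. The named predictors point to the first case, which is the more damaging: at an assumed 20% missing brand, shifts of 1.3 points (95% to 93.7%) and 3.6 points (70.4% to 74.0%). In the second case coverage at 20% is about 90–92%. At 5% missing the effect on intervals is small.

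All these sizes depend on assumed missingness, brand shares, follow-up and predictor strength. The expectation of full recording in section 9.7.5 and the warning in section 9.9 need to be reconciled, because they decide how likely the trigger is. The missing category for BMI, smoking and alcohol is a secondary and more debatable matter.

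**What to change.** **Primary analysis.** Do not impute brand. Keep 'vaccinated, brand unknown' as its own exposure category, and end brand-specific person-time at a dated dose of unknown brand. Leave vaccinated persons with no first-dose date out of the brand-specific vaccinated group, since they have no time zero, and report how many there are.

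**Sensitivity analysis.** Replace single imputation with multiple imputation (at least 20 imputations) of brand and dose order, with the event indicator and cumulative hazard in the model, combined by Rubin's rules. Dates are not imputed, so time zero and the matched sets need not be rebuilt for each imputation.

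**Secondary.** Beside the missing-category analysis, add one with multiply imputed BMI, smoking and alcohol, and state the missing-at-random assumption.

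**Text.** Reconcile sections 9.7.5 and 9.9 on the expected extent of missing brand.

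**Cost.** Some lost brand-specific person-time, slightly wider intervals, extra computing, and possibly informative censoring at unknown-brand doses, a worry that section 9.7.3.2 already raises for switchers. Precision can bear it. Table 1 gives each brand the whole population, so its probability of 1 is a best case, but the smallest case count in the illustration also suffices. Moderna would have 100,000 × 0.0006057 × 6 × 0.059 ≈ 21 cases. Keeping 80% leaves about 17, with SE ≈ √(1/17) = 0.24 (the unvaccinated term is negligible) and an upper limit of 0.059 × exp(1.96 × 0.24) ≈ 0.09, still far below 1.
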